#### 4.7 Justification of target sample size

The target sample size currently assumes an attrition rate of 10% at two years after index surgery. In practice, the power of the study will be increased by follow-up longer than two years for a proportion of participants and decreased by follow-up shorter than two years for a proportion (e.g. due to mortality, participants requesting to withdraw, or planned closures of loop ileostomies). These factors will be monitored as data accrues for the study, their consequences for the target sample size will be modelled and the target sample size revised if appropriate.

We have estimated the hazard ratio that the study will be able to detect for a range of scenarios. The incidence of PSH is unknown; we have considered incidences of 30% and 40% as plausible. Surgical methods of interest are used with varying frequencies and so we have considered the impact of a range of ratios for the use of technical variation when comparing one variation with another, i.e. ratios of 1:1, 1:2, 1:5, 1:10 and 1:20. The correlation of the exposure of interest with other covariates is also unknown and we considered the impact of a range of correlations (0, 0.3 and 0.5). The hazard ratios that can be detected from a study of 4000 participants at the 5% level (2-sided) are shown in **Table 3**. For simplicity, we have assumed a binary exposure variable. For multi-category exposures, we will assess the overall effect of the exposure; if we were to adjust the significance level from 5% to 2% to allow for comparisons between subcategories, the power reduces from 90% (80%) to 82% (68%).

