# Table 3:Hazard ratios detectable in the CIPHER study for a range of assumptions,
based on a cohort of 4,000 participants.

Ratio of presence:	Squared correlation	Incidence of	Hazard ratio	o detectable
absence of covariate	with other covariates	PSH	90% power	80% power
1:1	0 (i.e. unadjusted)	40%	1.18	1.15
	0.3		1.21	1.18
	0.5		1.26	1.22
	0 (i.e. unadjusted)	30%	1.21	1.18
	0.3		1.25	1.21
	0.5	1.30		1.26
1:2	0 (i.e. unadjusted)	40%	1.19	1.16
	0.3		1.23	1.19
	0.5		1.28	1.23
	0 (i.e. unadjusted)	30%	1.22	1.19
	0.3		1.27	1.23
	0.5		1.32	1.27
1:5	0 (i.e. unadjusted)	40%	1.24	1.21
	0.3		1.30	1.25
	0.5		1.36	1.30
	0 (i.e. unadjusted)	30%	1.29	1.24
	0.3	1.35		1.30
	0.5	1.43		1.36
1:10	0 (i.e. unadjusted)	40%	1.33	1.28
	0.3		1.40	1.34
	0.5		1.49	1.41
	0 (i.e. unadjusted)	30%	1.39	1.33
	0.3		1.48	1.40
	0.5	1.59		1.49
1:20	0 (i.e. unadjusted)	40%	1.46	1.39
	0.3		1.58	1.48
	0.5		1.71	1.59
	0 (i.e. unadjusted)	30% 1.55		1.46
	0.3		1.69	1.57
	0.5		1.86	1.71

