#### i. Bias due to confounding

Two extremes of practice are possible:

- (a) surgeons prefer some variants in surgical technique to others and apply their preferred variant to all of their patients, irrespective of the patients' characteristics;
- (b) surgeons use several variants in surgical technique and choose the variant for a particular patient according to the patients' characteristics or other factors.

In situation (a), we expect that the risk of bias due to confounding will not be a serious issue since all surgeons are likely to operate on a wide variety of patients, i.e. predictors *other than* variations in the way a surgeon creates a stoma will be distributed similar within all surgeons; if (a) can be shown, there is also the possibility of adjusting for potential predictors other than surgical variations using an instrumental variable, i.e. surgeon preference one or other surgical method [41]. In situation (b), the risk of bias due to confounding will be potentially serious and we are likely to have to control for confounding by conventional, multivariable methods since an instrumental variable is unlikely to be available. We will be able to distinguish between situations (a) and (b) on the basis of the surgical data accruing as the study progresses.

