## 5. Study methods

## 5.1 Participant recruitment

The care of patients undergoing large and small bowel elective surgery for cancer or for inflammatory bowel disease is co-ordinated in all centres by specialist multi-disciplinary teams (MDTs). The MDTs meet regularly and consider all patients on the basis of their relevant staging investigations and other assessments. As part of usual care, a SCN or a surgeon will meet a patient identified by the MDT as requiring resection and stoma formation before surgery. The SCN or surgeon will give information about the study (patient information leaflet, PIL) to potential participants. Patients will be given as long as possible to consider the study before being approached for consent (at least 24 hours for elective surgery and usually more than 24 hours for expedited surgery). On rare occasions when a theatre becomes unexpectedly available, patients undergoing expedited surgery may be asked for consent less than 24 hours after receiving information about the study. SCNs approaching patients will not consent a patient if he/she requests longer thinking time and this was not available; patients who are visibly distressed will not be approached for consent.

Patients may be consented retrospectively following their surgery, as well as prospectively. Retrospective consent will be sought from eligible patients when consent cannot be obtained preoperatively for example: when a final decision to form a stoma is not made until the patient is in theatre; and when there is not enough time to discuss or for patients to consider the study fully prior to surgery. Wherever possible, the patient will be informed about the study prior to their surgery.

We aim to recruit at least 70 NHS Trusts over a 12 month period. Participants will be recruited over 24 months. We anticipate that about 12000 patients will be screened during

this period, that 66% (n  $\approx$  8000) will be eligible and that 50% (n  $\approx$  4000) of eligible patients will consent to take part in the study. This equates to a recruitment rate of about 4 patients per centre / per month, although this average number will vary according to the workload of a centre. The proposed schema is shown in **Figure 1**.

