#### 5.10 Likely rate of loss to follow-up

In accordance with **Figure 1**, we expect that ≥90% of patients will complete follow-up or die within the minimum 2 year follow-up period, i.e. loss to follow-up of <10% for the primary outcome for reasons other than death. We will make all reasonable efforts to stay in contact with patients through the use of postal communication, email, text message and telephone. We will also use multiple sources to track participants during follow-up (see 5.4). About a further 15% are expected to die within two years; the reduced follow-up for these participants may impact on the power of the study to detect associations between PSH and surgical variants, depending on whether death occurs before or after ascertainment of a PSH. The impact of attrition due to death on the power of the study will be reviewed as data accrue to ensure that the study can address the objectives satisfactorily.

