#### 8. Statistical analyses

#### 8.1 Plan of analysis

The data will be analysed according to the intention to implement a surgical step and will be reported in accordance with the principles of the CONSORT guidelines (but not items relating to randomization). A detailed statistical analysis plan will be prepared prior to locking the database. The primary outcome, time to PSH (defined as the time when PSH confirmed by imaging) and secondary time-to-event outcomes, will be analysed using survival methods. The models will take account of the hierarchical structure of the data; i.e. participants, nested within surgeons nested within centres. The hazards of key predictors will be estimated, with 95% confidence intervals, after adjusting for important procedure, patient and surgeon confounding factors.

Exploratory analyses will be used to inform the choice of survival distribution (e.g. Weibull). The factors included in the model, the modelling strategy and the approach to handling correlated covariates will be documented in the statistical analysis plan. Participants free from a PSH at final follow-up will be censored. Follow-up will also be censored if bowel continuity is restored, if participants have a redo stoma or die. These circumstances leading to censoring may be informative and sensitivity analyses (setting survival times to the longest observed times) will be undertaken to assess the potential impact of informative censoring. Secondary continuous outcomes will be analysed using a mixed regression models, again taking account of the hierarchical structure of the data and the repeated measurements over time. Binary outcomes (e.g. complications) will be analysed using

logistic regression. If the frequency of the outcomes allows, these models will also take account of the hierarchical structure of the data.

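### Section 4.7 says 10% attrition is assumed, but every hazard ratio in Table 3 is calculated on the full 4,000 participants with none lost

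*Protocol*

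**What the plan says.** Section 4.7 opens with the assumption: "The target sample size currently assumes an attrition rate of 10% at two years after index surgery". It then says that follow-up longer than two years will raise power and shorter follow-up will lower it, and that these factors will be monitored and the target revised if appropriate.

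Table 3 follows, headed "Hazard ratios detectable in the CIPHER study for a range of assumptions" and described as "based on a cohort of 4,000 participants". It gives 60 detectable hazard ratios: five exposure ratios, three squared correlations with other covariates, two incidences (40% and 30%) and two powers (90% and 80%), at a two-sided 5% level.

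Section 5.1 shows where 4,000 comes from. About 8,000 patients should be eligible and 50% "of eligible patients will consent to take part in the study". So 4,000 is the number entering the cohort, before any loss. No larger recruitment target appears from which 4,000 could be the remainder.

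Section 5.10 expects loss below 10% for reasons other than death, and adds: "About a further 15% are expected to die within two years".

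**The concern.** Anyone reading 4.7 in order will take the 90% and 80% in Table 3 as net of 10% attrition. If the table was calculated on everyone recruited, that reading is wrong.

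Table 3 is all the protocol offers in support of 4,000. It is also the baseline against which 4.7 promises to model attrition and, if need be, revise the target. Whoever does that modelling must know whether 10% has already been taken off. If they assume it has, they will under-allow for losses. A later reader of a null technique comparison could likewise credit the study with slightly more power than the calculation supports.

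**Working it through.** **Inputs.** From 4.7 and Table 3: two-sided α = 5%, power 90% or 80%, N = 4,000, incidence I = 40% or 30%, exposure ratios 1:k with k = 1, 2, 5, 10, 20, and R² = 0, 0.3, 0.5 (the table labels these squared correlations, and the figures fit that reading). Attrition of 10% is from 4.7; deaths of 15% are from 5.10.

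**Formula.** HR = exp[(z₀.₉₇₅ + z_power) / √(D·p(1−p)(1−R²))], with D = N·I events and p = 1/(1+k). The sum of z values is 3.2415 for 90% power and 2.8016 for 80%.

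**Step 1: reproduce the plan's figures with no attrition.** D = 4,000 × 0.40 = 1,600 or 4,000 × 0.30 = 1,200.

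- First row (1:1, R² = 0, 40%): √(1,600 × 0.25) = 20. exp(3.2415/20) = 1.176 and exp(2.8016/20) = 1.150. Printed: 1.18 and 1.15.
- Last row (1:20, R² = 0.5, 30%): 1.862 and 1.711. Printed: 1.86 and 1.71.
- All cells: 57 of 60 agree to two decimals and all 60 lie within 0.006. The median N implied by the printed values is 3,996.

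**Step 2: repeat with 10% attrition.** N = 3,600, so D = 1,440 or 1,080.

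- First row: 1.186 and 1.159.
- Last row: 1.925 and 1.761.
- All cells: none of the 60 agrees to two decimals, and all 60 recomputed values are larger than printed.

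**Step 3: power at the printed hazard ratios.** If a fraction f of the tabulated events is observed, power = Φ(3.2415·√f − 1.96) in the 90% column and Φ(2.8016·√f − 1.96) in the 80% column.

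*Full loss.* Everyone lost contributes nothing, so f = 0.90: power is 86.8% and 75.7%.

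*Gradual loss, follow-up stopped at two years.* This assumes a constant hazard giving 40% at two years, λ = −ln(0.6)/2 = 0.2554 per year, and exponential loss reaching 10% at two years, μ = −ln(0.9)/2 = 0.0527 per year. The expected event proportion is λ/(λ+μ) × (1 − 0.6 × 0.9) = 0.829 × 0.46 = 0.381. So f = 0.381/0.40 = 0.953, and power is 88.6% and 78.1%. Starting from 30% incidence, f = 0.952 and power is almost the same.

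**Step 4: deaths and longer follow-up.**

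| Scenario (40% incidence) | f | Power at the 90% / 80% hazard ratios |
|---|---|---|
| 10% loss, full event loss | 0.90 | 86.8% / 75.7% |
| 10% loss, gradual, two years | 0.953 | 88.6% / 78.1% |
| 10% loss + 15% deaths, full event loss | 0.75 | 80.2% / 67.9% |
| 10% loss + 15% deaths, gradual, two years | 0.887 | 86.3% / 75.1% |
| 10% loss + 15% deaths, gradual, 2–4 years' follow-up | 1.12 | 92.9% / 84.2% |

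The last row assumes uniform recruitment over the 24 months in 5.1, follow-up of two to four years (4.1), and the same hazard continuing after year two. A hazard that falls after year two would shrink that gain.

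**The case against.** The strongest reply is that the net effect on power is not established. Section 8.1 analyses time to hernia with censoring, so a participant who is lost or dies still contributes until that point. Many participants will be followed beyond two years. Under a constant hazard, even 10% loss plus 15% deaths leaves more events than Table 3 assumes. This stands. A reader might infer that the study is underpowered for its stated hazard ratios, and the documents do not support that. They support only that the stated attrition allowance is absent from the table.

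The 30% and 40% could also be read as events observed among all recruited, which would absorb attrition. But 4.7 calls them the incidence of parastomal hernia and does not say so, and a separate 10% assumption would then do no work.

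Three further inferences are tempting:

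- *Deaths are wrongly omitted.* The 15% is in 5.10, which says its effect on power will be reviewed as data accrue; 4.7 also names mortality. That is an open deferral, not a contradiction.
- *Clustering is wrongly ignored.* Section 8.1 says "The models will take account of the hierarchical structure of the data", and Table 3 has no design effect. But surgeons who "apply their preferred variant to all of their patients" are one of two possible extremes in 4.8(i), not what is expected. The intraclass correlation and patients per surgeon are not given. If technique varies within surgeon, the cost may be small or absent.
- *Table 3 misstates power for objectives 5 and 6.* Those compare techniques among mesh recipients only, but the table does not claim to cover them, and no expected mesh use is given.

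It is also fair to say that Table 3 is a grid over an incidence declared unknown, and that the first row moves by only 0.01.

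**Conclusion.** The point holds as an inconsistency between a stated assumption and the calculation beneath it. Section 4.7 says 10% attrition is assumed; all 60 entries in Table 3 use 4,000 participants with none lost.

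On a two-year basis the cost is about 1 to 3 points at 90% power (to 87–89%) and 2 to 4 points at 80% power (to 76–78%). The lower figures, 86.8% and 75.7%, are a bound: they assume complete loss of the events of the 10%, with the same incidence among those lost as among the rest. The upper figures rest on a constant hazard and steady loss. Follow-up beyond two years could remove the shortfall or reverse it, and the protocol does not quantify it. The conclusion is that the table is misdescribed, not that 4,000 is too few.

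**What to change.** Keep the target at 4,000 and do one of two things in 4.7:

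1. Recompute Table 3 on 3,600 participants and label it a conservative two-year basis. The first row becomes 1.19/1.16 and the last row 1.93/1.76.
2. Leave the figures as they are, state that Table 3 excludes attrition, and reword the opening sentence so that it no longer implies that 10% is built in.

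Either costs a recalculated table or a changed sentence. No participants, procedures or analyses change; under the first option the detectable hazard ratios become slightly less favourable.

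Optional additions, as suggestions and not corrections: sensitivity rows, with assumptions stated, for the 15% deaths in 5.10, for two to four years' follow-up, for a design effect if technique proves to be fixed by surgeon, and for the mesh-only comparisons in objectives 5 and 6 once mesh use is known.

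### Section 4.7 says the sample size assumes 10% attrition at two years, but Table 3 and the power figures at the 2% level contain no attrition at all

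*Protocol*

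**What the plan says.** Section 4.7 opens its justification with "The target sample size currently assumes an attrition rate of 10% at two years after index surgery". It adds that longer follow-up will raise power, that mortality, withdrawal and planned closures will lower it, and that these effects will be monitored, modelled and the target revised if appropriate.

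On incidence it says "we have considered incidences of 30% and 40% as plausible"; on the frequency of surgical variants it takes "ratios of 1:1, 1:2, 1:5, 1:10 and 1:20". It then states: "The hazard ratios that can be detected from a study of 4000 participants at the 5% level (2-sided) are shown in" Table 3, whose title reads "based on a cohort of 4,000 participants". For comparisons between subcategories it says that moving from the 5% to the 2% level reduces power from 90% (80%) to 82% (68%).

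Section 5.1 shows what the 4,000 are: about 12,000 screened, about 8,000 eligible, and half "of eligible patients will consent to take part in the study". They are recruits, before any loss.

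Section 5.10 expects loss to follow-up below 10% for reasons other than death, and then: "About a further 15% are expected to die within two years".

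**The concern.** If 10% attrition is assumed and 4,000 is the number recruited, the calculation should rest on fewer events than 4,000 recruits with complete two-year follow-up would give. Table 3 names a cohort of 4,000 and shows no reduction. Either the allowance sits somewhere unseen, or the sentence is wrong.

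Table 3 is the protocol's only statement of detectable effects. Someone judging whether 4,000 is enough is told that a loss has been allowed for. If it has not, later monitoring of attrition would also start from the wrong baseline, because the first 10% of loss would be treated as already covered.

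**Working it through.** **Inputs.** Two-sided 5% level; N = 4,000; incidence 0.40 or 0.30; exposure ratio 1:k, so p = 1/(1+k); R² = 0, 0.3 or 0.5, as in the Table 3 column headed "Squared correlation"; power 90% and 80%. All come from section 4.7.

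**Reproducing Table 3.** The standard formula for a binary covariate in a survival model is

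HR = exp[(1.960 + z) / √(D · p(1−p) · (1−R²))], with z = 1.282 (90%) or 0.842 (80%) and D the number of events.

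Take D = 4,000 × incidence, so 1,600 or 1,200.

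- 1:1, R² = 0, 40%: 1,600 × 0.25 = 400, √400 = 20. HR = exp(3.242/20) = 1.176 and exp(2.802/20) = 1.150. Printed: 1.18 and 1.15.
- 1:20, R² = 0.5, 30%: 1,200 × (20/441) × 0.5 = 27.21. HR = 1.862 and 1.711. Printed: 1.86 and 1.71.

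Over the whole table 57 of 60 cells match to two decimals. The other three are in the 1:10, 30% block: 1.3847, 1.3249 and 1.5846 against 1.39, 1.33 and 1.59, a largest difference of 0.0054.

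**Testing for a hidden 10%.** With N = 3,600 (1,440 or 1,080 events) none of the 60 cells match, and every computed value exceeds the printed one. A least-squares search over N from 3,000 to 5,000 in steps of 10 fits best at 4,000. Close neighbours fit about as well (3,990 matches 59 cells), but 3,800 matches only 16. For the first cell at 3,600, Freedman's formula gives 1.187 and a one-sided 5% level 1.167, neither of which rounds to 1.18.

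**The 2% figures.** Φ(3.242 − 2.326) = 82.0% and Φ(2.802 − 2.326) = 68.3%, as printed. They start from 90% and 80% and so inherit the same omission.

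**Effect of the stated 10% on the two-year basis.** If a fraction f of the events remains, power at the printed hazard ratios is Φ[(1.960 + z)√f − 1.960].

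*Those lost contribute no events:* f = 0.90, power 86.8%/75.7%; at the 2% level 77.3%/63.0%.

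*Loss spread evenly (constant rates, an assumption):* hernia rate h = −ln(1 − incidence)/2, loss rate c = −ln(0.9)/2, events = 4,000 · h/(h+c) · [1 − exp(−2(h+c))].

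- 40%: h = 0.2554, c = 0.0527; 4,000 × 0.829 × (1 − 0.6 × 0.9) ≈ 1,525 events.
- 30%: h = 0.1783; 4,000 × 0.772 × (1 − 0.7 × 0.9) ≈ 1,143 events.
- f ≈ 0.953 and 0.952; power about 88.6%/78.1% (88.5%/78.0% at 30%). At the 2% level about 80%/66%.

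*Adding 15% deaths at a constant rate, −ln(0.85)/2 = 0.0813:*

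- 40%: 4,000 × 0.656 × (1 − 0.6 × 0.9 × 0.85) ≈ 1,420 events.
- 30%: 4,000 × 0.571 × (1 − 0.7 × 0.9 × 0.85) ≈ 1,061 events.
- f ≈ 0.887 and 0.884; power about 86%/75%.

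**Detectable hazard ratios at 90% power with N = 3,600.** 1.186 instead of 1.176 (1:1, R² = 0, 40%); 1.93 instead of 1.86 (1:20, R² = 0.5, 30%).

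**Correlation or squared correlation.** The text speaks of correlations of 0, 0.3 and 0.5; the table of squared correlations. Of the 40 cells with a non-zero value, 39 match when 0.3 and 0.5 are taken as R², and none match when they are squared first.

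**The case against.** The strongest objection is that Table 3 also leaves out follow-up beyond two years, which works the other way. The study schema gives 2 to 4 years, recruitment runs for 24 months (section 5.1), the study ends when the last participant reaches two years (section 5.3), and the primary outcome is time to hernia, analysed by survival methods (section 8.1). The constant-rate model above, with 10% loss and 15% deaths per two years plus uniform accrual (an assumption), gives about 1,787 and 1,375 events, more than the 1,600 and 1,200 in the table. If the hernia hazard halves after year two, events are about 1,618 and 1,227; if it falls to a quarter, power is about 88.5%/78%. Stoma closures would lower these figures. This stands: a reader might infer that the study's final power is overstated, and the documents do not support that. The net direction is open.

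Two further points stand in part. Survival analysis uses participants until they are lost, so 86.8%/75.7% is the pessimistic end, and section 5.10 treats 10% as a ceiling. Section 8.4 speaks of 30% to 40% of participants having developed a hernia at two years, which can be read as a crude proportion already net of deaths; the deaths calculation is therefore conditional. The limiting case in which the whole 25% contribute nothing (about 80%/68%) is not realistic and carries no weight here.

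The promise in section 4.7 to monitor and revise does not answer the point. It concerns departures in practice, whereas the 10% is said to be in the target already.

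**Conclusion.** The point holds as a mismatch between a stated assumption and the printed figures. Table 3 contains no attrition, and neither do the 82% and 68% derived from its power levels.

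On the table's own two-year basis the shortfall is about 1.4 to 3.2 percentage points at 90% power and 1.9 to 4.3 at 80%. It becomes about 4 and 5 points if deaths are added at constant rates and the 30% and 40% are not already net of them. These sizes rest on proportional hazards, a binary exposure, and the loss and death patterns stated above.

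The shift in detectable hazard ratios is small beside the 1.15 to 1.86 that Table 3 spans. Nothing here shows that 4,000 is too few.

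**What to change.** Any one of three changes removes the mismatch:

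- Recompute Table 3 and the 2%-level power on the events expected after the stated 10% loss and the expected deaths. Either include the planned 2 to 4 years of follow-up, with its assumptions on accrual and late hazard, or say that it is excluded. State whether 30% and 40% are net of deaths.
- Keep the hazard ratios and restate the power on the two-year basis, with the loss pattern assumed.
- Keep Table 3, delete the claim that 10% is assumed, and say that the table makes no allowance for attrition, deaths or follow-up beyond two years.

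In the same edit, change correlations to squared correlations in the text of section 4.7.

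The cost is one table or one or two sentences. No study procedure changes, and recruitment need not change on this ground alone.

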#### 2. Background

In the UK approximately 20,000 new stomas are created annually [1]. Within two years of the initial stoma formation, up to 40% of patients may have developed a PSH. This means that there is a swelling next to the stoma whereby abdominal contents protrude underneath the skin. While some PSHs are asymptomatic, it is thought that at least 50% are associated with problems. The most common symptoms are pain (35%) and difficulty attaching the stoma appliance (28%) [3]. This may result in the leakage of bowel contents (28%), which can cause skin irritation, anxiety and embarrassment [3]. Some patients require emergency

admission to hospital due to bowel obstruction, strangulation or perforation. This may necessitate surgery, potentially including revision of the stoma, which can be associated with the development of further PSH. Prevention of PSH is therefore a priority. Indeed this was recently supported by a Delphi survey of the Association of Coloproctology of Great Britain and Ireland (ACPGBI), who ranked optimisation of methods to prevent and repair PSH as a key research question [4].

The NIHR has funded the UK Cohort study to Investigate the prevention of Parastomal Hernia (CIPHER). CIPHER is designed with two parts (Phase A and B). Phase A involves essential preliminary work before the cohort study can take place (Phase B). Phase A will identify the data that should be collected in order to investigate the prevention of PSH. This includes information about surgical technique (Part 1) and development of a patient-reported outcome measure (Part 2).

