## 2. Background

## 2.1 The clinical problem

The prevalence of all types of abdominal stomata in the UK is about 100,000 and 20,000 new stomata are created annually [1]. However, the incidence of PSH is more difficult to assess due to a lack of prospective data and heterogeneity in how clinical and symptomatic PSH are defined. In the current literature, rates of PSH of up to 40% have been reported, varying according to follow-up duration, stoma type and diagnosis method.

To date a variety of methods have been used to diagnose PSH both clinically and symptomatically. Clinically, PSH has been diagnosed from intra-operative findings, clinical examination and computerised tomography (CT). Clinical examination has poor inter-observer reliability [2] and the European Hernia Society (EHS) considers CT to be best way to detect PSH when following up patients with stomata [3]. However, an 'anatomical' PSH detected by CT may not cause symptoms. Symptomatic PSH have typically been identified from health-related quality of life (HRQoL) assessments but the appropriateness of using particular HRQoL tools to detect problems specific to PSH is uncertain. Regardless of the method of clinical or symptomatic diagnosis, PSH can have substantial physical, psychological and economic consequences.

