## 2.2 The burden of PSH

## 2.2.1 The physical and psychological burden of PSH

PSH are common and are symptomatic for at least 75% of patients. Pain (35%), difficulties attaching stoma bags with associated leakage of bowel contents (28%) and peristomal skin irritation are the commonest problems [4]. Bowel strangulation, obstruction and perforation may also be related to PSH and are rare but serious [5]. In addition, PSH reduces HRQoL and causes limitations in sexual function, travel, social interaction and return to work [6]. Despite advances in stoma care, the proportion of patients with symptoms has remained largely unchanged over the past 20 to 30 years [6].

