#### 4.6 Primary and secondary outcomes

#### 4.6.1 Primary outcome

The primary outcome will be PSH incidence during follow-up after index surgery to form a stoma. An incident PSH is defined as:

- Symptoms of PSH (see 5.4), and
- Anatomical PSH, ascertained by independent reading of a CT scan (6)

Participants will describe their PSH symptoms using a custom-designed questionnaire, the "stoma questionnaire" [34]. Symptoms will be classified as green (asymptomatic), amber (mild/moderate symptoms) or red (severe symptoms). Cut-off points for these classifications will be defined on the basis of on-going data collection. We anticipate that severe symptoms may include recurrent problems with the stoma appliance, pain, or admission to hospital with obstruction. Mild/moderate symptoms are likely to be associated with discomfort and ill-fitting appliance issues managed by the patients themselves.

CT scans carried out in the course of a patient's usual NHS care will be assessed for all participants, with anatomical PSH being graded using the EHS classification (EHS class I, II, III or IV [24]). CT scans taken up to 6 months before or 3 months after the stoma questionnaire is completed will be valid for assessing anatomical PSH. The combination of symptomatic PSH and anatomical PSH confirmed by CT imaging will be our primary outcome. CT assessors will collect additional details from CTs (e.g. linear measurement of the PSH defect rather than just defect size >5cm vs ≤5cm), including a measure of the size of the PSH. The ESH criteria for classifying PSH as small or large will be reviewed on the basis of these additional data as the study progresses.

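### Table 3's 30% and 40% incidences are not tied to the composite primary outcome: the 40% rows look too high for it, and no scenario below 30% is shown

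*Protocol*

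**What the plan says.** All places are in the Phase B protocol unless stated.

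- **Outcome (section 4.6.1).** "The combination of symptomatic PSH and anatomical PSH confirmed by CT imaging will be our primary outcome". The CT must be a usual-care scan taken no more than 6 months before or 3 months after a stoma questionnaire. Sections 5.2 and 11.2.1 confirm that the study itself performs no scan.
- **Incidence used for power (section 4.7).** "The incidence of PSH is unknown; we have considered incidences of 30% and 40% as plausible". The hazard ratios in Table 3 are for 4,000 participants at the two-sided 5% level, with exposure ratios from 1:1 to 1:20.
- **Where 40% appears elsewhere.** Section 2.1 reports that "rates of PSH of up to 40% have been reported", varying with length of follow-up, stoma type and method of diagnosis. Section 1 gives about 40% within 2 years. Section 8.4 uses 30% to 40% for participants who develop a PSH. None of these is limited to symptomatic, CT-confirmed hernias.
- **Symptomatic share.** Section 2.2.1: "PSH are common and are symptomatic for at least 75% of patients". The Phase A protocol, section 2, is lower: "it is thought that at least 50% are associated with problems".
- **Planned review.** Section 4.7 will revisit the target for length of follow-up, mortality, withdrawal and stoma closure. Section 5.10 adds attrition from death. Neither mentions symptomatic share or CT capture.

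**The concern.** The detectable hazard ratio depends on the number of primary-outcome events. The composite is a subset of all PSH: section 2.1 itself says that a hernia seen on CT may cause no symptoms, and a symptomatic patient without a usable scan cannot be counted. Yet the top incidence in Table 3 equals the protocol's figure for PSH of any kind, and no factor for symptoms or for availability of a scan is shown.

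The study exists to compare surgical variants, some of them uncommon enough that 1:20 is tabulated. If composite events are fewer than assumed, a null result for such a variant could be read as evidence from a well-powered comparison when it is not.

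**Working it through.** **1. Reproduce Table 3.** Inputs from section 4.7: N = 4,000, two-sided α = 0.05, power 90% or 80%, exposure prevalence p = 1/2, 1/3, 1/6, 1/11 or 1/21, R² = 0, 0.3 or 0.5. With D = N × incidence (Schoenfeld formula with covariate adjustment):

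HR = exp{ (z₁₋α/₂ + z_power) / √[D·p(1−p)(1−R²)] }, where the z sum is 3.2415 for 90% power and 2.8016 for 80%.

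- 40%, 1:1, R² = 0: D = 1,600, √(1,600 × 0.25) = 20, so exp(3.2415/20) = 1.18 and exp(2.8016/20) = 1.15. Printed: 1.18 and 1.15.
- 30%, 1:20, R² = 0.5: D = 1,200, p(1−p) = 20/441, √(1,200 × 20/441 × 0.5) = 5.216, giving 1.86 and 1.71. Printed: 1.86 and 1.71.

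All 60 entries reproduce to within 0.005. Events are therefore exactly 4,000 × 40% = 1,600 or 4,000 × 30% = 1,200, with nothing further removed. (The 10% attrition is not in these counts either; that is a separate matter.)

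**2. Composite incidence.** Composite = PSH rate × symptomatic share × share with a valid CT. With complete CT capture:

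- 40% × 75% = 30%, which is Table 3's lower scenario
- 30% × 75% = 22.5%
- 40% × 50% = 20%
- 30% × 50% = 15%

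**3. Power at the hazard ratios printed in the 40% rows.** If events are a fraction f of those assumed, power = Φ(3.2415√f − 1.96) for the 90% column and Φ(2.8016√f − 1.96) for the 80% column. At f = 0.75 (30% instead of 40%) these are Φ(0.847) = 80% and Φ(0.466) = 68%.

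**4. CT capture.** The protocol gives no rate. As an assumption, 80% capture turns 30% into 24%, and 60% turns it into 18%. Against the 40% rows, f is then 0.60 (power about 71% and 58%) or 0.45 (about 59% and 47%).

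**5. Detectable hazard ratios for 4,000 participants (90% / 80% power).**

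| Composite incidence | Events | 1:1, R² = 0 | 1:20, R² = 0.5 |
|---|---|---|---|
| 40% (printed) | 1,600 | 1.18 / 1.15 | 1.71 / 1.59 |
| 30% (printed) | 1,200 | 1.21 / 1.18 | 1.86 / 1.71 |
| 24% | 960 | 1.23 / 1.20 | 2.00 / 1.82 |
| 22.5% | 900 | 1.24 / 1.21 | 2.05 / 1.86 |
| 18% | 720 | 1.27 / 1.23 | 2.23 / 2.00 |
| 15% | 600 | 1.30 / 1.26 | 2.41 / 2.14 |

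**The case against.** A good case can be made for the table as printed.

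- Section 4.6.1 defines an incident PSH as the composite shortly before section 4.7 speaks of PSH incidence, so 30% and 40% may be meant as composite rates. Nothing labels them as rates of any PSH.
- On Phase B's own figures 40% × 75% = 30%, so the lower scenario can already be the composite, and the step from 90% to 80% power is then visible in the table: at 1:1 unadjusted, 1.18 stands under 90% power at 40% and under 80% power at 30%.
- The 75% and 50% are floors. A PSH rate of 35% with 86% symptomatic also gives 30%.
- Follow-up runs from 2 to 4 years, and literature rates from mixed diagnostic methods are not a proven ceiling for PSH read on CT.
- Section 5.4 intends to review at least one scan in each year of follow-up. With six-monthly questionnaires the 9-month windows overlap, so the window alone should exclude few scans if questionnaires are returned.

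Most of this stands, and it limits the point. A reader might infer that every row is overstated, or that 30% is an optimistic case presented as the pessimistic one. The documents do not show either: both readings need 30% to be a rate of any PSH, or a symptomatic share or CT capture that the protocol does not give. The arithmetic is also not at fault.

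Three things survive. First, at the 75% floor with full capture, a 40% composite would need a PSH rate of 0.40/0.75 = 53%. At a 40% PSH rate it needs every hernia to be symptomatic and scanned. Second, intending to review a scan each year does not mean that usual care will supply one, and a participant with none cannot be an event. Third, no row covers a composite incidence below 30%.

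**Conclusion.** The incidence input to Table 3 is not linked to the outcome it is meant to power. If 40% is the rate of PSH in general, as it is everywhere else in the protocol, the 40% rows overstate power unless essentially every PSH is symptomatic and CT-captured. At the 75% floor with complete capture, 90% and 80% become about 80% and 68%.

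The 30% rows are not shown to be wrong. They hold if PSH rate × symptomatic share × CT capture reaches 30%, for example 40% × 75% × 100%.

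Below that the shortfall is a range. At 22.5% the 90%-power hazard ratio is 1.24 (1:1, unadjusted) and 2.05 (1:20, R² 0.5). The 15% case (1.30 and 2.41) pairs the Phase A floor of 50% with the lower incidence, so it is the low end of the scenarios with complete capture and not the expected one. The 24% and 18% cases rest on assumed capture of 80% and 60%.

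**What to change.** In section 4.7:

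1. State the assumed composite incidence as PSH rate × symptomatic share × share with a valid CT in the window, with a value and basis for each.
2. Relabel the 40% rows as any-PSH incidence, or drop them.
3. Add rows below 30%, for example 24%, 22.5%, 18% and 15%, with detectable hazard ratios for 4,000 participants as in the working table, extended to the other exposure ratios and R² values.
4. Add symptomatic share and CT capture to the factors followed in the planned review of the target sample size.

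The cost is a recalculated table and a short paragraph. The stated hazard ratios become less favourable; conduct of the study is unchanged.
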